##### b) Proportion of patients with at least one hospital admission

i) H0i: There is no difference in the proportion of patients who report a hospital readmission for day i (null hypothesis); H1i: The proportion of patients who report a hospital readmission for the standard discharge group is greater than that for the enhanced discharge group; for days  $i = 3, 7, 14, 21, 30, 60, 90$ .

- ii) We will assess the groups for differences using logistic regression.
- 2) Emergency department visits
- a) Number of emergency department visits
    - i) H0i: There is no difference in the cumulative number of ED visits for day i (null hypothesis); H1i: The cumulative number of ED visits for the standard discharge group is greater than that for the enhanced discharge group; for days  $i = 3, 7, 14, 21, 30, 60, 90$ .
    - ii) We will assess the groups for differences using Poisson regression model.
  - b) Proportion of emergency department visits
    - i) H1i: The proportion of patients who report at least one ED visits for the standard discharge group is greater than that for the enhanced discharge group; for days  $i = 3, 7, 14, 21, 30, 60, 90$ .
    - ii) We will assess the groups for differences using logistic regression model.
- 3) Primary care provider (PCP) visits
- a) Number of PCP visits
    - i) H0i: There is no difference in the cumulative number of PCP visits for day i (null hypothesis); H1i: The cumulative number of PCP visits for the standard discharge group is greater than that for the enhanced discharge group; for days  $i = 3, 7, 14, 21, 30, 60, 90$ .
    - ii) We will assess the groups for differences using Poisson regression model.
  - b) Proportion of PCP visits
    - i) H0i: There is no difference in the proportion of patients who report at least one PCP visits for day i (null hypothesis); H1i: The proportion of patients who report at least one PCP visits for the standard discharge group is greater than that for the enhanced discharge group; for days  $i = 3, 7, 14, 21, 30, 60, 90$ .
    - ii) We will assess the groups for differences using logistic regression model.
- 4) Physical health as measured by the Short Form (SF12) functional health score

- a) Hoi: There is no difference in mean SF-12 Physical Health scores between the standard and enhanced discharge groups (null hypothesis); H1i: The mean SF-12 Physical Health scores differ between the standard and enhanced discharge groups.
  - b) We will use a repeated measures ANOVA model (over the 7 time periods) to model the SF-12 Physical Health score as a function of treatment group.
- 5) Mental Health as measured by the Short Form (SF12) Mental Health Score
- a) Hoi: There is no difference in mean SF-12 Mental Health scores between the standard and enhanced discharge groups (null hypothesis); H1i: The mean SF-12 Mental Health scores differ between the standard and enhanced discharge groups.
  - b) We will use a repeated measures ANOVA model (over the 7 time periods) to model the SF-12 Mental Health score as a function of treatment group.
- 6) Care Transition Measure (CTM3) of discharge coordination services
- a) Hoi: There is no difference in mean CTM3 scores between the standard and enhanced discharge groups (null hypothesis); H1i: The mean CTM3 scores differ between the standard and enhanced discharge groups.
  - b) We will use a repeated measures ANOVA model (one time period at 3 days post discharge) to model to assess these hypotheses.
- 7) Rural Transition Measure (RTM14) of the delivery of transition services and supports
- a) H0: There is no difference in the mean RTM14 score between the standard and enhanced discharge groups (null hypothesis); H1: Patients in the enhanced discharge group will have a higher mean RTM14 rating than patients in the standard discharge group.
  - b) We will use a repeated measures ANOVA model (over the 6 time periods) to model the RTM14 score as a function of treatment group.

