## Demographic Characteristics of Study Sample Required for Clinical Trials

	Baseline A	Intervention	Baseline B	Totals
Enrolled	63	50	14	127
Completed	62	47	13	122
Lost to Follow-up	1	3	1	5
Under 18 Years of Age	0	0	0	0
Between 18 and 65	37	26	10	73
Over 65	26	24	4	54
Female	28	21	6	55
Male	35	29	8	72
American Indian, Alaskan	5	6	2	13
Asian	0	0	0	0
Hawaiian or Islander	1	0	0	1
Black or African American	0	0	0	0
White	56	43	11	110
More than one race	0	0	0	0
Unknown or Not Reported	1	1	1	3
Subtotal	63	50	14	127
Hispanic or Latino	0	0	0	0
Not Hispanic or Latino	61	47	11	119
Unknown or Not Reported	2	3	3	8
Subtotal	63	50	14	127

In addition, Table 3 presents the number of patients excluded by criterion and Table 4 shows the number of patient enrolled in the study from each county by experimental condition.

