### ***Design***

We used a quasi-experimental time series design with switching replications (Cook & Campbell, 1984). This design involved starting enrolled patients from each of the four counties in a baseline condition. Then, once a stable rate of enrollment had been reached, the introduction of the experimental procedures was staggered across patients from each county over time. That is, all patients from one county were enrolled into the intervention while those from the other counties remained in baseline. Later, patients from a second and third county were added to the intervention condition while those from the remaining county remained in baseline; and so on. Finally, a return to baseline condition was initiated for patients from all

four counties. This design protects against most threats to the internal validity of findings and many threats to their external validity. It is particularly helpful in protecting against threats posed by seasonal variables. A final "return to baseline" phase was also included in the study to add to protections from threats posed by interactions.

**Baseline and experimental conditions.** Patients in baseline conditions received the standard discharge services. Patients enrolled in the experimental condition received the standard discharge services and the Enhanced Discharge Planning and Rural Transition Supports.

**Measures.** All patients completed the PAM10 (Hibbard & Mahoney, 2005) and provided selected demographic information at the time of enrollment. Other demographic information was collected from each enrolled patient's medical record. In addition, we collected the LACE+ rating from the medical record and the rating of needs from our Rural Transition Needs Assessment. The LACE+ is a compilation of medical and treatment factors (e.g., chronic conditions, previous hospitalizations) derived from a patient's medical record that are used to assess risk for re-hospitalization (van Walraven, Wong, & Forster, 2012).

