#### 1) Hospital re-admissions

##### a) Number of hospital admission

i) H0i: There is no difference in the cumulative number of hospital admissions for day i (null hypothesis); H1i: The cumulative number of hospital admissions for the standard discharge group is greater than that for the enhanced discharge group; for days  $i = 3, 7, 14, 21, 30, 60, 90$ .

ii) We will assess the groups for differences using Poisson regression model.

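### The SAP names neither a test statistic nor a sparse-data method for its logistic and Poisson models, though a group with no events is a real possibility at the earliest days

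*Combined protocol and SAP*

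**What the plan says.** The Statistical Analysis Plan section makes hospitalizations and emergency department visits the subject of the primary hypotheses. Each is analysed as a cumulative count (1a, 2a) and as a proportion with at least one event (1b, 2b). A separate hypothesis is set for each day, "i = 3, 7, 14, 21, 30, 60, 90".

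- Counts (1a, same wording in 2a): "We will assess the groups for differences using Poisson regression model".
- Proportions: "We will assess the groups for differences using logistic regression" (1b) and "We will assess the groups for differences using logistic regression model" (2b).
- Direction: the alternatives are one-sided. For 1b: "The proportion of patients who report a hospital readmission for the standard discharge group is greater than that for the enhanced discharge group".

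Nothing further is said about these models. The SAP does not say whether tests are Wald, score or likelihood-ratio. It gives no exact or penalised alternative, minimum event count, expected event rate or alpha.

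Table 2 gives the group sizes for Baseline A, Intervention, Baseline B and the total: "Enrolled 63 50 14 127" and "Completed 62 47 13 122".

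**The concern.** Few patients may have been readmitted or have visited an emergency department by day 3 or day 7. If one group has no event, the maximum-likelihood log odds ratio or log rate ratio has no finite value. If both groups are empty, there is no group effect to estimate. The plan does not say what would be reported in either case.

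An empty enhanced group is the most favourable result the intervention can produce, and an effective intervention makes it more likely. The conclusion would then depend on which default test the software prints, a choice that the SAP leaves open and that could be made after seeing the data. Each day-specific test is affected on its own, so a multiplicity adjustment would not repair it.

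**Working it through.** **Inputs.** Table 2 gives 63 + 14 = 77 standard and 50 enhanced patients, total 127. Pooling the two baselines is an assumption. It fits the two-group hypotheses and the Design section ("Patients in baseline conditions received the standard discharge services"), but the SAP does not state it. Event risks are not in the documents and are assumed below. The plan gives no figure on this point to reproduce.

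**Step 1: chance of an empty group.** With cumulative risks p0 (standard) and p1 (enhanced):

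P(at least one empty) = (1−p0)^77 + (1−p1)^50 − (1−p0)^77 × (1−p1)^50.

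At 2% in both groups: 0.211 + 0.364 − 0.211 × 0.364 = 0.498.

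| Standard-group risk | Equal risk | Enhanced risk half as large |
|---|---|---|
| 1% | 79% | 88% |
| 2% | 50% | 69% |
| 3% | 29% | 52% |
| 4% | 17% | 39% |
| 5% | 9% | 30% |
| 8% | 1.7% | 13% |

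Both groups are empty with probability (1−p)^127 at equal risk: 28% at 1% and 8% at 2%. With completers only (62 + 13 = 75 v 47), the 2% row becomes 52% and 71%.

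**Step 2: which days.** As an illustration, assume a constant hazard, so that risk by day d is 1 − (1−R)^(d/30) for a 30-day risk R. Chance of at least one empty group:

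| R | Day 3, equal | Day 7, equal | Day 7, enhanced half | Day 14, equal |
|---|---|---|---|---|
| 10% | 77% | 40% | 61% | 11% |
| 15% | 60% | 20% | 42% | 2.5% |
| 20% | 45% | 9% | 29% | 0.6% |
| 25% | 32% | 4% | 20% | 0.1% |

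Day 3 is exposed across this range. Day 7 depends on the assumption. From day 14 the problem fades.

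**Step 3: what the stated models return.** Take 3/77 v 0/50.

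- *Wald.* The logistic fit stops at a log odds ratio near −21 with a standard error near 18,500. Two-sided p is 0.999, so one-sided p in the SAP's direction is about 0.50. The Poisson fit behaves the same way. A Wald test cannot reject however many events the other group has.
- *Likelihood ratio, logistic.* 2 × [3 ln(3/77) + 74 ln(74/77) − 3 ln(3/127) − 124 ln(124/127)] = 3.05; the signed root is 1.75 and one-sided p is 0.040.
- *Likelihood ratio, Poisson.* With 3 events v 0: 2 × 3 × ln(127/77) = 3.00; one-sided p is 0.042.
- *Fisher exact, one-sided.* C(77,3)/C(127,3) = 73,150/333,375 = 0.22.
- *Exact conditional Poisson, one-sided.* (77/127)^3 = 0.22.

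**Step 4: error rate of the likelihood-ratio test.** No alpha is stated; a one-sided 5% is assumed. Summing the binomial probabilities of all outcomes (a/77, b/50) at which the signed-root p is below 0.05 gives a type I error of 7.3%, 9.2%, 8.8% and 7.7% at equal risks of 2%, 3%, 4% and 5%. At 1% it is 2.6%, because three events are then rarely reached. The same sum for the Wald test stays below 0.4% at all these risks.

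**Step 5: what a sparse-data method gives.** For a 2×2 table the Firth estimate equals adding 0.5 to each cell. For 3/77 v 0/50 the odds ratio is (0.5/50.5)/(3.5/74.5) = 0.21, with an approximate 95% interval of 0.01 to 4.2. One-sided Fisher p is C(77,a)/C(127,a) for a/77 v 0/50: 0.078 at a = 5 and 0.046 at a = 6. At least 6/77 v 0/50 is therefore needed for an exact one-sided p below 0.05.

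**The case against.** A reader might infer that the planned analysis is a Wald test that will report p near 1. The documents do not support this. The SAP never names the Wald test, and its alternatives for these outcomes are one-sided, so an empty enhanced group gives a Wald p of about 0.5. A reader might also infer that empty groups will often occur at days 3 and 7. That too goes beyond the documents, which give no early risk for admissions or emergency visits; the two may differ, and at 8% equal risk the chance is only 1.7%.

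The strongest defence is that a likelihood-ratio test from the same models is finite with one empty group, so the plan is incomplete rather than wrong. This stands only in part. The test is finite but exceeds its assumed nominal level at risks of 2% to 5%, and it leaves the point estimate and one confidence limit infinite. The two usual readings of the stated model therefore fail in opposite directions.

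It is also fair to say that little power is lost. A clear-cut table such as 7/77 or more v 0/50 has probability 0.03% at 2% in both groups and 1.3% at 4% v 2%, and an exact test would rarely reject at these days either. This stands and limits the consequence. So does the point that only the earliest of the seven days are much exposed and that nothing in the SAP singles them out.

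**Conclusion.** The concern holds in limited form. For primary hypotheses 1a, 1b, 2a and 2b, the SAP specifies ordinary logistic and Poisson regression at days where a group may have no events, and leaves both the test and the handling of sparse data open. With 77 v 50 patients, an empty group is about an even chance at 2% equal risk and more likely than not below that, or at 3% v 1.5%. This makes it likely at day 3 if cumulative risk is about 2% or less, uncertain at day 7, and of little weight later.

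The conclusion rests on pooling the two baselines, on assumed event risks, on a group-only model as the SAP's wording implies, and, for the error rates, on an assumed one-sided 5% level. It is worth correcting because it touches the primary outcomes and the remedy is standard; it does not undermine the later time points.

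**What to change.** State in the SAP, for 1b and 2b, that the day-specific proportions are analysed by Firth penalised-likelihood logistic regression with profile-likelihood intervals, or by exact conditional logistic regression. For 1a and 2a, state that an exact conditional Poisson test or a penalised Poisson model is used when events are sparse, and define sparse in advance. Any numerical cut-off, including one for descriptive reporting only, is a convention to be fixed before outcomes are examined. Keep the one-sided direction of the stated hypotheses, name the alpha, say whether the two baselines are pooled, and say that no effect is estimated when both groups are empty.

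The cost is a few sentences of SAP wording. Firth estimates carry slight shrinkage, and exact methods are somewhat conservative. If outcome data have already been seen, the change should be labelled as made afterwards.

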**Enhanced discharge and rural transition planning.** Researchers engaged patients and other stakeholders in a structured process of contextual assessment and innovation to develop an Enhanced Discharge and Rural Transition model, protocol, and procedures (separate manuscript that can be cited). Figure 2 outlines the components of both the standard practice and the enhanced model. Researchers added 11 components to the standard practices, including: a Rural Transitions Needs Assessment, a resource bank for each rural community linked to categories of the needs assessment, a Patient Transition Agenda, an electronic episode of care in Epic® to support patient transition, patient-centered communication procedures between SPH staff and Local Community Transition Coordinators (LCTC), a discharge orders verification procedure, a transitions planning protocol, transitions follow-up procedures, a long-range goals assessment also linked to community resources, communication procedures to alert the patient's PCP of their hospitalization and transition home, and a coordination mechanism between LCTCs at the CAHs and the Research Discharge Coordinators at the RRH to facilitate teamwork.

[figure not shown]

Figure 2: Tentative model describing the Enhanced Discharge and Rural Transitions Process. The shaded boxes at the top of the figure represent the standard practice. The open boxes at the bottom represent the experimental procedures. All patients received the standard procedures. Patients in the experimental conditions also received the enhanced procedures.

In general, the enhanced model was based on the existing discharge planning protocol but extended it by creating new roles and functions that focused on addressing patient needs that might interfere with recovery at home. Procedurally, a Research Transitions Coordinator located at the regional referral hospital used a tablet computer to conduct a Rural Transitions Needs Assessment with a patient. The patient's identified needs were linked to services and supports listed in a Community Resource Bank. Together, these formed a patient's Transition Agenda. The RTC posted the Agenda in an Episode of Care (EOC) tab in Epic®.

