Items rated "2" or less were treated as potential patient needs. If a patient rated an item as "2" or less, the RTC would ask, “Can you tell me a bit more about this?” She would record responses as additional information. If a patient rated an item as 3 or higher (or NA) but that rating seemed incongruent with information learned from the file review or discussion with the patient, the RTC would ask, “Can you tell me more about how you will meet that

need?” This prompt sometimes led to a change in rating. Again, these explanatory responses were recorded as additional information. LCTCs used this additional information in preparing the draft Transitions Plan.

The patient’s endorsed needs were linked to a database of resources, the Local Resource Bank, known to provide services and supports in identified areas of need. Together, the needs and linked services created a patient Transition Agenda (PTA). Figure 4 shows a sample Patient Transition Agenda.

Figure 4: A screen shot of a patient's Transition Agenda listing services available in his hometown that he could use to address each identified need in the areas of medication, home modifications, and rehabilitation services.

**Electronic Episode of Care.** The RTC posted the patient's Transitions Agenda in the EOC tab in Epic® and notified (via EPIC® in-basket email and phone) the LCTC serving the county to which the patient was scheduled to return that a patient from the county was being treated at SPH and provided an estimated date of discharge. This early involvement, a component insisted on by the key stakeholders from the CAHs, allowed the LCTC to review a patient's treatment, risk factors, likely needs, and available resources to meet those needs while the patient was still in the hospital. In addition, the LCTC reviewed the patient’s AVS in EPIC and prepared a Discharge Orders Verification Checklist that listed orders and recommendations for the patient's recovery at home (e.g., medications, oxygen orders, etc.).

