**Verifying discharge orders and scheduling a Transitions Conference.** Once discharged home (or to a swing bed placement), the LCTC contacted the patient to check on his or her status and to schedule a Transition Conference. The LCTC used the brief Discharge Orders Checklist to review the status of each discharge order with a patient. This was completed simply by asking the patient to indicate that an order had been implemented or not. If the checklist revealed any immediate gaps in implementation, the LCTC could take action to help the patient address any obstacles in securing the services. If no immediate gaps were identified, the LCTC scheduled a Transitions Conference with the patient. Then, the LCTC notified the patient's primary care provider (PCP) that one of their patients had been treated at SPH, had enrolled in the Enhanced Discharge and Rural Transitions study, and provided directions for locating the patient's Episode of Care tab in Epic®.

**Patient Transitions Conference.** The Patient Transition Conference involved the LCTC meeting with the patient in their home to review the Transitions Agenda and develop a Transitions Plan. While the preferred setting for the Transitions Conference was the patient's home, this meeting could also take place at the local CAH or even over the phone. Meeting at the patient's home was preferred because it was seen as helping the LCTC to understand a patient better and thought to lead to recognition of needs not previously identified. It was also seen as helping the LCTC judge what types of supports are most likely to fit the patient's context; thus, be more likely to be followed by the patient and caregivers. Furthermore, the Patient Design Team unanimously and strongly encouraged its inclusion in the model.

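### The PCP-visit alternatives (3a, 3b) predict fewer visits under enhanced discharge, with no rationale, alpha or sidedness, so an increase falls outside the prespecified hypothesis

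*Combined protocol and SAP*

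**What the plan says.** Statistical Analysis Plan, item 3, has two parts, each tested at days 3, 7, 14, 21, 30, 60 and 90.

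- 3a, number of visits. The null is no difference. The alternative is "The cumulative number of PCP visits for the standard discharge group is greater than that for the enhanced discharge group". The method line is "We will assess the groups for differences using Poisson regression model".
- 3b, proportion with at least one visit. The alternative again begins "The proportion of patients who report at least one PCP visits for the standard discharge group is greater", and the method is logistic regression.

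The direction is the same as for hospital admissions (item 1) and emergency department visits (item 2). Other items differ. For SF-12 physical health (item 4) the alternative is "The mean SF-12 Physical Health scores differ between the standard and enhanced discharge groups", and SF-12 mental health and CTM3 follow that form. For RTM14 (item 7) it is "Patients in the enhanced discharge group will have a higher mean RTM14 rating than patients in the standard discharge group".

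The opening of the Statistical Analysis Plan names hospitalizations and emergency department visits as the subject of the primary hypotheses, then lists intermediary outcomes. PCP visits are in neither list. No significance level and no sidedness are stated anywhere.

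**The concern.** Fewer admissions and fewer emergency visits are an obvious aim of a transition programme. Fewer primary care visits are not, and the document offers no argument for expecting them. Several enhanced components could plausibly bring patients to their PCP more often, and an alternative that counts only a fall as support excludes that result.

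The wording also pulls two ways. The alternative is directional, while the method line speaks only of assessing differences. Without a stated sidedness, the same data could be reported as one-sided or two-sided. A rise in PCP visits could be dismissed as not significant, or declared significant while contradicting the written hypothesis. A fall would be read as supporting the intervention.

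**Working it through.** **1. The intervention set beside the hypothesis.**

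- Under Procedures (enhanced discharge and rural transition planning), one added component is a communication procedure to alert the patient's "PCP of their hospitalization and transition home".
- Under Electronic Episode of Care, the local coordinator "prepared a Discharge Orders Verification Checklist that listed orders and recommendations" for recovery at home.
- Under the subsection on verifying discharge orders, the coordinator goes through those orders with the patient and, where there are gaps, "could take action to help the patient address any obstacles in securing the services". The same subsection has the coordinator notify the PCP after discharge.
- In standard care the After Visit Summary may already carry a follow-up referral. Checking orders could therefore turn referrals into visits.

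None of this states an expected direction. It makes an increase at least as plausible as a decrease.

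**2. Inputs for an illustration.** The plan gives no power calculation, alpha or PCP visit rate, so there is no figure to reproduce.

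- From Table 2: standard 63 + 14 = 77 (both baselines pooled), enhanced 50.
- Assumed: independent patients, no county or period effects, 5% level, μ visits per standard patient, true rate ratio RR (enhanced over standard). A one-sided test is also an assumption.

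**3. Counts (3a).** Wald test on the log rate ratio:

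SE = √[1/(77μ) + 1/(50μ·RR)], δ = ln(RR)/SE

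One-sided rejection in the stated direction = Φ(−1.645 − δ). Two-sided power ≈ Φ(δ − 1.96).

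For μ = 1.5 and RR = 1.3:

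- Expected visits: 77 × 1.5 = 115.5 and 50 × 1.5 × 1.3 = 97.5.
- SE = √(1/115.5 + 1/97.5) = 0.1375, and δ = 0.2624/0.1375 = 1.908.
- One-sided: Φ(−3.553) = 0.0002. Two-sided: Φ(−0.052) = 0.48.

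Simulation of the same test (400,000 replicates) over a range of μ, at RR = 1.3:

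| μ | One-sided, stated direction | Two-sided |
|---|---|---|
| 0.1 | 1.1% | 7% |
| 0.2 | 0.8% | 10% |
| 0.5 | 0.3% | 20% |
| 1.0 | 0.07% | 34% |
| 1.5 | 0.02% | 48% |
| 2.5 | 0.003% | 69% |

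The closed form agrees to within about one percentage point.

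Sensitivity of the two-sided power at μ = 1.5 and 2.5:

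- RR = 1.1: 10% and 14%.
- RR = 1.3, completers only (62 + 13 = 75 v 47): 46% and 67%.
- RR = 1.3, variance twice Poisson (δ divided by √2): 27% and 41%.

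**4. Proportions (3b).** Wald test on the log odds ratio, 77 v 50:

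| Standard v enhanced | One-sided, stated direction | Two-sided |
|---|---|---|
| 60% v 75% | 0.03% | 41% |
| 60% v 70% | 0.3% | 20% |
| 50% v 60% | 0.3% | 19% |

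**5. One data set, two reports.** Suppose 60% v 80% were observed in 77 and 50 patients.

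- Pooled proportion = (77 × 0.60 + 50 × 0.80)/127 = 0.679.
- SE = √[0.679 × 0.321 × (1/77 + 1/50)] = 0.0848, so z = 0.20/0.0848 = 2.36.
- The one-sided p in the stated direction is 0.99. The two-sided p is 0.018.

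**6. Power cost if a decrease was truly expected.** At RR = 0.77, moving from one-sided to two-sided lowers power from 49% to 37% (μ = 1.5) and from 68% to 56% (μ = 2.5), about 12 percentage points.

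**The case against.** The strongest reply is that nothing shows the direction to be wrong. The PCP notification informs the provider and points to the record; it does not ask for or book a visit. The checklist examples are medications and oxygen orders, not appointments. The three utilisation outcomes share one direction, which may be deliberate. This stands: the finding is an unexplained direction, not a demonstrated error or a copying slip.

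A second reply is that the null of no difference and the method line lean towards two-sided testing. On that reading a rise could reject the null, and the regressions would estimate it either way. This also stands, and the very small one-sided figures apply only under a rule the plan never states. Even so, a rise would contradict the written alternative, and the plan does not say which reading applies.

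Third, alpha and sidedness are missing throughout the Statistical Analysis Plan, not only here. That is true, but it does not remove the problem specific to PCP visits, where the direction is also unexplained.

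Finally, the document already reports enrolment and completion, so rewording now could itself look post hoc. That is a fair caution, and it is why the change needs a date and a disclosure.

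**Conclusion.** The concern holds. Both PCP alternatives are directional without a rationale, and an increase, which the plan's own intervention makes at least as plausible as a decrease, cannot count as support. If the test is one-sided as worded, a true 30% increase would be declared about 1% of the time or less across the assumed rates. If it is two-sided, power for that increase runs from 7 to 10% at 0.1 to 0.2 visits per standard patient (as might apply at the early days) to 48 to 69% at 1.5 to 2.5 visits.

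These sizes rest on assumed visit rates, a 5% level and independent Poisson counts. Extra variation lowers the power. Confidence is high about the wording and the missing rule; the documents do not establish which direction to expect. The point should be corrected, but it does not touch the primary conclusions.

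**What to change.** Restate 3a and 3b so that the alternative is a difference between the groups in the number, or the proportion, tested two-sided at a stated alpha. The plan already uses this form for SF-12 and CTM3. Report the rate ratio (3a) or odds ratio (3b) with its confidence interval at each reported day. Date the change and say whether outcome data had been seen when it was made.

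If the sponsor prefers the present direction, add the reason for expecting fewer PCP visits and state the sidedness of the test.

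The cost is a wording change and a dated disclosure, with no new data, plus the power loss shown above if a decrease was genuinely the expectation. Two-sided wording resolves the direction problem only. Power stays low at the early days and for small effects, so the interval estimates should carry the interpretation there.
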